8.1.2 Definition of Serious Adverse Events (SAE)

The serious adverse events for the study and control agent can be found on the attachment of the agents' package insert.

Serious Adverse Event

Adverse events are classified as serious or non-serious. A **serious adverse event** is any AE that is:

- fatal
- life-threatening
- requires or prolongs hospital stay
- results in persistent or significant disability or incapacity
- a congenital anomaly or birth defect
- an important medical event

Important medical events are those that may not be immediately life threatening, but are clearly of major clinical significance. They may jeopardize the subject, and may require intervention to prevent one of the other serious outcomes noted above. For example, drug overdose or a seizure that did not result in in-patient hospitalization, or intensive treatment of bronchospasm in an emergency department would typically be considered serious.

All adverse events that do not meet any of the criteria for serious should be regarded as **non-serious adverse events**.

8.1.3 Definition of Unanticipated Problems (UP)

Unanticipated Problems Involving Risk to Subjects or Others

Any incident, experience, or outcome that meets all of the following criteria:

- Unexpected in nature, severity, or frequency (i.e. not described in study-related documents such as the IRB-approved protocol or consent form, the investigators brochure, etc)
- Related or possibly related to participation in the research (i.e. possibly related means there is a reasonable possibility that the incident experience, or outcome may have been caused by the procedures involved in the research)
- Suggests that the research places subjects or others at greater risk of harm (including physical, psychological, economic, or social harm).

8.2 Classification of an Adverse Event

8.2.1 Severity of Event

For AEs not included in the protocol defined grading system, the following guidelines will be used to describe severity.

- **Mild** – Events require minimal or no treatment and do not interfere with the participant's daily activities.

CONFIDENTIAL

This material is the property of the NYU School of Medicine and Langone Medical Center. Do not disclose or use except as authorized in writing by the study sponsor

- **Moderate** – Events result in a low level of inconvenience or concern with the therapeutic measures. Moderate events may cause some interference with functioning.
- **Severe** – Events interrupt a participant’s usual daily activity and may require systemic drug therapy or other treatment. Severe events are usually potentially life-threatening or incapacitating.

8.2.2 Relationship to Study Agent

For all collected AEs, the clinician who examines and evaluates the participant will determine the AE’s causality based on temporal relationship and his/her clinical judgment. The degree of certainty about causality will be graded using the categories below.

- **Definitely Related** – There is clear evidence to suggest a causal relationship, and other possible contributing factors can be ruled out. The clinical event, including an abnormal laboratory test result, occurs in a plausible time relationship to drug administration and cannot be explained by concurrent disease or other drugs or chemicals. The response to withdrawal of the drug (dechallenge) should be clinically plausible. The event must be pharmacologically or phenomenologically definitive, with use of a satisfactory rechallenge procedure if necessary.
- **Probably Related** – There is evidence to suggest a causal relationship, and the influence of other factors is unlikely. The clinical event, including an abnormal laboratory test result, occurs within a reasonable time after administration of the drug, is unlikely to be attributed to concurrent disease or other drugs or chemicals, and follows a clinically reasonable response on withdrawal (dechallenge). Rechallenge information is not required to fulfill this definition.
- **Possibly Related** – There is some evidence to suggest a causal relationship (e.g., the event occurred within a reasonable time after administration of the trial medication). However, other factors may have contributed to the event (e.g., the participant’s clinical condition, other concomitant events). Although an AE may rate only as “possibly related” soon after discovery, it can be flagged as requiring more information and later be upgraded to “probably related” or “definitely related,” as appropriate.
- **Unlikely to be related** – A clinical event, including an abnormal laboratory test result, whose temporal relationship to drug administration makes a causal relationship improbable (e.g., the event did not occur within a reasonable time after administration of the trial medication) and in which other drugs or chemicals or underlying disease provides plausible explanations (e.g., the participant’s clinical condition, other concomitant treatments).
- **Not Related** – The AE is completely independent of study drug administration, and/or evidence exists that the event is definitely related to another etiology. There must be an alternative, definitive etiology documented by the clinician.

8.2.3 Expectedness

The information on the insert package for both the study and the control agent will be responsible for determining whether an AE is expected or unexpected. An AE will be considered unexpected if the nature, severity, or frequency of the event is not consistent with the risk information previously described for the study agent.

8.3 Time Period and Frequency for Event Assessment and Follow-Up

The occurrence of an AE or SAE may come to the attention of study personnel during study visit or during the remote follow up period. All AEs including local and systemic reactions not meeting the criteria for SAEs will be captured. Information to be collected includes event description, time of onset, clinician’s assessment of severity, relationship to study product (assessed only by those with the training and authority to make a diagnosis), and time of resolution/stabilization of the event. All AEs occurring while on study must be documented appropriately regardless of relationship. All AEs will be followed to adequate resolution.

Any medical condition that is present at the time that the participant is screened will be considered as baseline and not reported as an AE. However, if the study participant’s condition deteriorates at any time during the study, it will be recorded as an AE. UPs will be recorded in the data collection system throughout the study.

CONFIDENTIAL

This material is the property of the NYU School of Medicine and Langone Medical Center. Do not disclose or use except as authorized in writing by the study sponsor

Changes in the severity of an AE will be documented to allow an assessment of the duration of the event at each level of severity to be performed. AEs characterized as intermittent require documentation of onset and duration of each episode.

The PI will record all reportable events with start dates occurring any time after informed consent is obtained until the last day of study participation. At each study visit, the investigator will inquire about the occurrence of AE/SAEs since the last visit. Events will be followed for outcome information until resolution or stabilization.

All unresolved adverse events should be followed by the investigator until the events are resolved, unless the subject is lost to follow-up, or the adverse event is otherwise explained. At the last scheduled visit, the investigator should instruct each subject to report any subsequent event(s) that the subject, or the subject's personal physician, believes might reasonably be related to participation in this study.

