Endpoints	
Primary Study Endpoint
 
 • Oral health related quality of life OHIP-14 score changes from preoperative to postoperatively on day 1 and day 5. 
Secondary Study Endpoints
 
 • Postoperative pain intensity during 5 days • Number and type of pain medication use • Duration of LA in hours (numbness) after receiving pulpectomy/endodontic debridement 
Exploratory Endpoints
 
 • Cold test results (+/-) • Number of supplemental injections • Duration until adequate lip numbness is obtained (in minutes) • Duration until negative cold response is obtained (in minutes)
Study Duration	The estimated duration of this study is 1 year
Participant Duration	4 weeks ± 10 days (until the second appointment with the subject)
Duration of IP administration	
The duration of administration of either Bupivacaine or Lidocaine as an inferior alveolar nerve block (IANB) lasts up to two minutes.
 
The duration of anesthesia following administration is up to 7 hours for Bupivacaine and up to 4 hours for Lidocaine.

Population	Patients presenting to the NYU Dentistry Department of Endodontics for endodontic care for a symptomatic mandibular molar tooth, aged between 18-85 years, any gender, all demographic and ethnic groups and ASA I or II.
Study Sites	NYU College of Dentistry Department of Endodontics
Number of Participants	We plan to enroll 50 subjects in each group; approximately 100 participants will be enrolled. 20% dropout rate is expected, with an expected 40 subjects in each group.
Description of Study Agent/Procedure	Bupivacaine is an FDA approved anesthetic drug, commercially available (0.5% Bupivacaine with 1:200,000 epinephrine) routinely administered intraorally by IANB.
Reference Therapy	Lidocaine is an FDA approved anesthetic drug, commercially available (2% Lidocaine with 1:100,000 epinephrine) routinely administered intraorally by IANB.
Key Procedures	Preoperative data collection, administration of an IANB (Bupivacaine or Lidocaine), followed by standard of care 1 st visit endodontic procedure; pulpectomy/endodontic debridement. Postoperative data collection during 5 days after treatment.

CONFIDENTIAL

[figure not shown]
This material is the property of the NYU School of Medicine and Langone Medical Center. Do not disclose or use except as authorized in writing by the study sponsor

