The solutions also contain sodium metabisulfite, a sulfite that may cause allergic-type reactions including anaphylactic symptoms and life-threatening or less severe asthmatic episodes in certain susceptible people. The overall prevalence is very low. Subjects who have sodium metabisulfite allergies will be excluded from the study.

Any adverse reaction that could be caused by bupivacaine is similar, if not identical, to lidocaine because both have a similar chemical composition, both are amide type LA, and both are commonly and interchangeably used in dental practice (10, 27). With all routine precautions taken, exceeding the recommended plasma level and reaching toxic concentrations thus the occurrences of adverse events are reported to be rare during dental treatments.

When the study agent, bupivacaine HCl 0.5% with epinephrine, is used for dental injections, the long duration of anesthesia (7 hours) could increase the possibility of inadvertent biting trauma to tongue, lips, and buccal mucosa. Subjects will be advised not to chew solid foods or test the anesthetized area by biting or probing until normal sensation has returned. Subjects may have difficulty in eating, drinking, talking for a longer period of time, which might affect them physically and psychosocially. However, postoperative pain may also limit subjects' orofacial functioning and wellbeing, which is eliminated by LLA. Therefore, the information to be gained regarding the overall efficacy of bupivacaine by using OHIP-14 is significant and outweighs the risks involved.

Subjects will be asked to spend time filling out questionnaires before and after treatment. We have limited the amount of questions per document to save the subject time. Subjects can complete these questionnaires alone if preferred, or if the subject feels uncomfortable answering any of the questions, they can tell the study coordinator or the PI. Although there is a minor risk for loss of privacy in this study, confidential data collected for research purposes will be labeled with a unique de-identified study subject number and stored securely.

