5.6 Duration of Study Participation

The duration of study participation will be from the 1st treatment visit, until the participant returns for their second routine endodontic treatment visit. At this second visit, compensation will be given and data collection will be finalized if necessary. This is in an effort to coincide the research visit with the routine and required dental visit. This visit will be scheduled by the treating dentist and can be scheduled up to several weeks after the first treatment visit. There will be no time limit for this research visit. If the patient will return to the school for an appointment in another department/clinic, they can inform the research team and efforts will be made to meet the patient then if the 5 days post-treatment data collection is complete.

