After the adequate lip numbness is gained, another 10 minutes will be waited to achieve pulpal anesthesia; Cold Test – As per standard of care, Endo-Ice (Coltene, USA) will be administered to subjects to determine the success of pulpal This is a routine step in endodontic treatment. A cotton pellet is sprayed with the refrigerant spray and applied the tooth. A painful response will indicate inadequate pulpal anesthesia.

Subjects in each group will also receive a buccal infiltration and IL injection with Lidocaine which is highly recommended for symptomatic teeth. The Cold Test will be repeated to determine anesthesia. The algorithmic chart for anesthetic administration in the supplementary form *Pulpectomy/Endodontic Debridement Method* will be followed as the guideline. Additional supplemental injections will be administered as portrayed in the chart with Lidocaine HCl 2% 1:100,00 in both groups if needed, until pulpal anesthesia is obtained to initiate treatment, without jeopardizing the maximum dose limit for the subject.

Subjects who need supplemental injections more than 2 times will be excluded the study.

4. Intra- and Immediate Post-operative Data Collection:

- Pre-operative data obtained after clinical and radiographic examination which are performed as standard of care, before the treatment procedure, such as cold test response, percussion hypersensitivity, pulpal and periapical diagnosis will be collected by a study investigator by the end of the treatment, together with the intraoperative and immediate postoperative data.
- Intraoperative data such as number of cartridges used, time for adequate anesthesia, additional supplementary anesthesia will be collected.
- Intraoperative pain will be evaluated on a NRS by asking the subject directly after treatment.

5. Remote Data Collection:

Subjects will receive surveys remotely either by e-mail through REDCap, which will ask about their pain intensity reported on an NRS, analgesic medication use and numbness. REDCap surveys will be sent at 6, 12, 24, 48, 72, 96 and 120 hours after treatment. On day 1 and 5, subjects will be assessed by OHIP14.

If subjects do not have access to the Internet, a study team member will call them. Paper questionnaires will also be an option if no other methods are convenient for subjects. If they prefer to fill in the questions and questionnaire on paper, they will be asked to bring them to their second appointment.

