7.2.3 Remote Data Collection

Subjects will be asked to rate their pain intensity on an NRS, report analgesic use and numbness:

- 6 hours after treatment
- 12 hours after treatment
- 24 hours after treatment
- 48 hours after treatment
- 72 hours after treatment
- 96 hours after treatment
- 120 hours after treatment

- Day 1 – OHIP14 questionnaire

- Day 5 – OHIP14 questionnaire

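### After discharge, adverse events are next asked about at a second visit some 18 to 38 days later, so early biting injuries are likely to be under-recorded

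*Combined protocol and SAP*

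**What the plan says.** - **When adverse events are asked about.** Section 8.3: "At each study visit, the investigator will inquire about the occurrence of AE/SAEs since the last visit". Between visits the wording is passive: "The occurrence of an AE or SAE may come to the attention of study personnel during study visit or during the remote follow up period". Events are recorded from consent to each subject's last day of participation.
- **Which visits exist.** After the treatment day there is one, the second endodontic appointment (section 7.2.4). The Protocol Summary gives participant duration as 4 weeks ± 10 days, ending at that appointment. Sections 5.6 and 6.1.8 let the treating dentist set it up to several weeks out and then say: "There will be no time limit for this research visit". They also allow the closing contact to take place at an appointment elsewhere in the school once the five-day data are in.
- **What the remote contacts cover.** Section 7.1.1 describes surveys "which will ask about their pain intensity reported on an NRS, analgesic medication use and numbness", sent at 6, 12, 24, 48, 72, 96 and 120 hours. Section 7.2.3 agrees: "Subjects will be asked to rate their pain intensity on an NRS, report analgesic use and numbness". Both add OHIP-14 on day 1 and day 5. Neither lists an adverse event or injury item.
- **Paper users.** Section 7.1.1: "If they prefer to fill in the questions and questionnaire on paper, they will be asked to bring them to their second appointment".
- **The named risk.** Section 2.4.1 says that the long numbness with bupivacaine, put at 7 hours, "could increase the possibility of inadvertent biting trauma to tongue, lips, and buccal mucosa".
- **What uses the records.** Section 8.5 halts the study on a count of reported grade 3 events judged probably related. Section 8.4 requires immediate reporting to the IRB. Section 10.2.8 plans no safety analysis.

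**The concern.** The injury that the protocol itself links to the longer-acting drug happens at home, in the hours after discharge. The team contacts the subject seven times in the following five days but, on the protocol's description, never asks about it. The first planned question comes weeks later, when a bitten lip or cheek has probably healed and been forgotten.

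Two things are at stake. First, section 8.3 undertakes to capture all adverse events, with time of onset, time of resolution and the duration at each severity level. Recall after several weeks cannot reliably supply that for a minor soft-tissue injury. Second, the halting count in section 8.5 and the immediate reporting in section 8.4 both work on events the team knows about, so an event learnt only on enquiry enters them late.

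**Working it through.** The protocol gives no figure for how completely adverse events will be captured. The check is therefore a comparison of the passages plus arithmetic on the visit window. The sample size calculation does not enter.

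**Inputs**
- Second visit: 28 ± 10 days (Protocol Summary), or no limit (sections 5.6 and 6.1.8).
- Risk period for biting trauma: about 7 hours = 7/24 = 0.29 day (section 2.4.1).
- Remote contacts: 6, 12, 24, 48, 72, 96 and 120 hours, seven in all, the last on day 5 (sections 7.1.1 and 7.2.3).
- Enrolment: 100 subjects; study duration 1 year (Protocol Summary).

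**Step 1: time to the first enquiry after discharge.** 28 − 10 = 18 days and 28 + 10 = 38 days. The recording period varies between subjects by a factor of 38/18 = 2.1. Sections 5.6 and 6.1.8 set no upper bound. They also allow an earlier close-out once the five-day data are complete, but do not say whether that meeting counts as a study visit for section 8.3.

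**Step 2: recall for an injury at about 7 hours.** 18 − 0.29 = 17.7 days and 38 − 0.29 = 37.7 days.

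**Step 3: gap after the last remote contact.** 18 − 5 = 13 days and 38 − 5 = 33 days. In that interval the protocol schedules no contact.

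**Step 4: delay in the halting count.** Assume 100 subjects are enrolled evenly over 365 days, or 100/365 = 0.274 per day. While an event known only by enquiry waits to be learnt, 0.274 × 18 = 4.9 to 0.274 × 38 = 10.4 further subjects are enrolled, so about 5 to 10. If the second visit slipped to an assumed 60 or 90 days, the figures would be 16.4 and 24.7. The one year is the whole study, so enrolment itself would be faster and these counts somewhat higher.

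**Step 5: the same quantities with a question at 120 hours.** Recall is 5 − 0.29 = 4.7 days, and 0.274 × 5 = 1.4 subjects are enrolled meanwhile.

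**Step 6: what the existing contacts would pick up.** The numbness item runs to 120 hours and would show prolonged anesthesia. OHIP-14 on days 1 and 5 would show its functional burden. As described, neither records an injury, its onset or its resolution.

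**The case against.** The strongest case against has five parts.

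**Subjects can report events themselves.** They are told to call the PI if analgesics do not help (section 7.6). Unscheduled visits record symptoms, including swelling (section 7.2.6). Persistent anesthesia is to be reported to the PI (section 10.1.2), and the consent copy carries the PI's contact details (section 13.3.1). This stands: weeks-long recall is the default for an unreported event, not a certainty. But every one of these routes needs the subject to act, and a minor bite is unlikely to prompt a call. A reader might also infer that nobody can act on severe pain or lasting numbness in a paper user. The documents do not support that: paper is a last-resort option, and those subjects have the same routes. Only their written answers arrive late.

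**The effects of numbness are measured.** Section 2.1 chose OHIP-14 partly to capture what prolonged numbness does to patients, and it is collected at two fixed early times. This stands for function, not for injury.

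**Swelling is a weak example.** Section 2.4.1 describes it as transient and near the injection site, and the subject is observed during treatment. This stands; biting trauma is the clear gap.

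**The survey form was not available.** It is an attachment listed in section 18. The point rests on two consistent descriptions of it. If the form has an adverse event item, sections 7.1.1 and 7.2.3 should say so.

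**Asking early could harm the trial.** Section 10.1.2 breaks the individual's blind when an adverse event occurs. A question at 24 hours could unblind subjects before the day-5 primary endpoint, and more often on bupivacaine if it does cause more bites. This stands and determines where the question should go.

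**Conclusion.** The point holds in a limited form. On the protocol's description, biting trauma after discharge is recorded only if the subject volunteers it or recalls it about 18 to 38 days later, so under-recording is likely. Events known only by enquiry reach the halting count late, by about 5 to 10 enrolled subjects under even accrual. A single bite may never meet the section 8.5 criteria, so the delay matters mainly for the process as a whole.

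Three stronger readings are tempting and are not supported.
- *The benefit-harm comparison is biased toward bupivacaine.* No safety comparison is planned (section 10.2.8). Equal forgetting in both arms would shrink an absolute difference in bites, but nothing in the documents gives its size.
- *Unequal windows spoil the adverse event counts.* The windows do vary, but nothing shows that they vary by arm, and no planned analysis uses time at risk.
- *Recall is unlimited.* The absence of a limit sits beside several weeks in section 5.6 and 4 weeks ± 10 days in the Protocol Summary. These passages must be reconciled; they do not establish unlimited recall.

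The primary analysis is not affected. The change should be made but is not essential. The conclusion assumes that the survey form matches its two descriptions and that minor injuries are poorly recalled after some weeks.

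**What to change.** 1. Add one standard item at the end of the 120-hour contact, after the day-5 OHIP-14 and the pain, medication and numbness items are complete: *Since treatment, have you bitten or injured your lip, cheek or tongue, or had swelling or any other new problem? (describe, with day of onset)*.
2. For subjects on paper, ask it through the phone route that section 7.1.1 already provides for those without internet, once they have filled in the day-5 forms.
3. State in section 8.3 that events solicited through 120 hours are tabulated by arm as a common window, and that recording to the end of participation continues as now.
4. Ask the item earlier, for example at 24 hours, only if the unblinding text in section 10.1.2 is first reconciled with keeping subjects blinded through the day-5 primary endpoint.
5. Reconcile the Protocol Summary with sections 5.6 and 6.1.8 on the timing of the second visit.

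**Cost.** One survey item, a short call to each subject on paper, and one amended paragraph; the sample size does not change. About 5 days of recall remain. More minor events will have to be recorded, reported under section 8.4 and handled under section 10.1.2. Because the item comes after the last remote outcome, unblinding at that point cannot affect the remote outcomes already collected.
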